5.4 STRATEGIES FOR RECRUITMENT AND RETENTION

Recruitment and retention strategies for Aims 1 and 3

Approximately 4800 participants will be recruited from 100 primary care clinics affiliated with six PBRNs. Each PBRN has centrally-based research coordinators with a history of success working in PBRN practices, documented expertise in previous large diagnostic or therapeutic trials, and personnel experienced in recruitment and data collection.

IRB approval will be obtained at each PBRN for approval for patient contact, informed consent and participation in this study.

All patients who meet all inclusion and no exclusion criteria at the participating PBRN clinical site will be eligible for participation. Research coordinators will work with participating practices to identify and approach potential participants. Recruitment strategies may vary depending on the practice.

Enrollment of participants will depend on the gender, ethnic and racial makeup of those that are being recruited from the practices included in this trial. No exclusion criteria apply specifically to women or to minorities. The Data Coordinating Center (DCC) will track enrollment of participants throughout the course of this study. If women and minorities are under-represented in the initial phase of recruitment, a commitment exists to develop recruitment strategies that target these populations so the final study group is a well-balanced representation of the studied population.

Recruitment and retention strategies for Aim 2

Clinician participants: Approximately 150 clinic participants are recruited by: 1) introductory telephone contact with the practice leadership by PBRN research coordinators and the aim 2 research team; 2) follow up letter, time commitment infographic and informed consent forms sent to interested practices outlining aim 2 clinician participant activities and responsibilities; and 3) in-person aim 2 study explanation to clinician participants at the committed practices during the introductory baseline study site visit.

Clinician participant recruitment draws from both prescribing (or “provider”) staff and non-prescribing (or “clinical support”) staff. The aim 2 research team will attempt to obtain an even mix of both clinician staff types from each practice. Retention incentive of clinician participants over 2 years includes provision of on-line COPD education to all clinician participants and monetary incentive to practices as determined by each individual PBRN.

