9.1.1.1 SENSITIVITY AND SPECIFICITY OF THE CAPTURE TOOL

Primary Hypothesis 1. The CAPTURE tool will exhibit excellent sensitivity and specificity in diagnosing clinically significant COPD as defined by post-bronchodilator FEV₁/FVC < 0.70 in addition to either ≥1 exacerbation-like event (ECOPD) within the past 12 months or an FEV₁ < 60% predicted. Approximately 5000 patients will be enrolled in the study with the expectation that 300-800 of these will have previously undiagnosed clinically significant COPD, identified through research spirometry and documentation of prior respiratory events. Amongst cases, we will calculate the proportion of individuals who are at high risk for clinically significant COPD based on CAPTURE (sensitivity). Similarly, amongst non-cases, we will calculate the proportion of individuals not classified as having clinically significant COPD based on CAPTURE (specificity). Corresponding 95% confidence intervals will be calculated.

Based on our preliminary data drawn from a research setting, we noted 89.7% sensitivity and 93.1% specificity for CAPTURE. Table 9-1 shows the range of sensitivity and specificity 95% confidence interval widths that would result if the true sensitivity or specificity is 85%, 90% or 95% across a range of sample sizes. For instance, if we find 500 individuals with confirmed clinically significant COPD and CAPTURE has 90% sensitivity, then the 95% confidence interval for sensitivity would be 90% ± 2.6%. Similarly, if 4,000 individuals are confirmed to have no evidence of clinically significant COPD and CAPTURE has 90% specificity, then the 95% confidence interval for specificity would be 90% ± 0.9%.

| | | Sensitivity or Specificity | | |
|-------------|--|----------------------------|--------|--------|
| Sample Size | | 85% | 90% | 95% |
| 5000 | | ± 1.0% | ± 0.8% | ± 0.6% |
| 4000 | | ± 1.1% | ± 0.9% | ± 0.7% |
| 1000 | | ± 2.2% | ± 1.9% | ± 1.4% |
| 500 | | ± 3.1% | ± 2.6% | ± 1.9% |
| 250 | | ± 4.4% | ± 3.7% | ± 2.7% |
| 100 | | ± 7.0% | ± 5.9% | ± 4.3% |
| 50 | | ± 9.9% | ± 8.3% | ± 6.0% |

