9.1.2 SECONDARY OBJECTIVES

9.1.2.1 SENSITIVITY AND SPECIFICITY IN PREDEFINED SUBGROUPS

| Table 9-3. Projected numbers of clinically significant COPD cases and non-cases we expect by subgroup of interest assuming prevalence of obstructed individuals is between 6-16%. (*Non-Hispanic) This table assumes prevalence of non-clinically significant COPD similar to clinically significant COPD (not included in this table). | | | | | | | | | | |
|--|-------------|-------------|-------------|--------------|--------------|----------------|-------------|-------------|--------------------|---------------------|
| | Total | Men (50%) | Women (50%) | White* (62%) | Black* (15%) | Hispanic (18%) | Rural (46%) | Urban (54%) | Ever-Smokers (40%) | Never-smokers (60%) |
| Projected # confirmed clinically significant COPD by subgroup | 300-800 | 150-400 | 150-400 | 186-496 | 45-120 | 54-144 | 138-368 | 162-432 | 120-320 | 180-480 |
| Projected # confirmed no COPD by subgroup | 3,400-4,400 | 1,700-2,200 | 1,700-2,200 | 2,108-2,728 | 510-660 | 612-792 | 1,564-2,024 | 1,836-2,376 | 1,360-1,760 | 2,040-2,640 |

We will also examine several subgroups of interest that are key to addressing our overall goal of defining the value of CAPTURE across a broad range on individuals. These will include sex, ethnic groups, rural and urban location, and educational level, among individuals with clinically significant COPD, spirometrically defined COPD and individuals with “mild” COPD as defined in this protocol. We have specifically chosen clinical sites with a diverse gender, racial and ethnic mix, and rural and urban mix with the expected prevalence of clinically significant COPD cases and controls by subgroup outlined in Table 9-3, again with corresponding sensitivity and specificity confidence interval widths in Table 9-1. For example, if sensitivity of CAPTURE in Hispanic individuals is 90%, then a sample size of approximately 100 would give a confidence interval of $90\% \pm 5.9\%$. We believe that with an overall sample size of 5,000 recruited patients we will have adequately sized subgroups to assess the operating characteristics of CAPTURE in the subgroups of interest.

9.1.2.2 FURTHER ANALYSIS OF ASSOCIATIONS BETWEEN MEETING COMPOSITE ENDPOINT AND INDIVIDUAL AND PRACTICE LEVEL OUTCOMES

Secondary analyses for evaluating practice behavior are exploratory, and therefore not included in a formal power and sample size analysis. These analyses are described further in Section 9.3.2.

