The clinical trial component (Aim 3) of the CAPTURE study is a cluster-randomized trial of 100 primary care practices affiliated with seven practice-based research networks (PBRNs). Randomization to one of two interventions takes place at the practice level. Both interventions provide clinicians in participating practices with basic COPD education (enhanced usual care). Clinicians from practices randomized to the CAPTURE intervention additionally receive an educational module (CAPTURE education) on the CAPTURE tool. Each of the 100 practices is expected to enroll 50 patients (5000 total patients). In a single visit, each enrolled patient participant completes CAPTURE screening, pre- and post-bronchodilator spirometry and completes demographic, and general and respiratory related health questionnaires. Practices randomized to the CAPTURE intervention are provided with patient-level CAPTURE tool results for the patients it has enrolled in the study. One-year follow-up chart reviews and participant surveys are used for a pre-identified subset of participants to assess whether CAPTURE screening and sharing of results with clinicians results in higher rates of guideline-concordant COPD care in those with a positive CAPTURE tool result (CAPTURE+). Study investigators hypothesize that providing CAPTURE screening results to primary care clinicians will increase rates of COPD diagnosis and increase guideline concordant COPD care.

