Patients who are eligible and agree to participate in the study sign informed consent, complete the CAPTURE questionnaire, PEF testing, spirometry testing, other respiratory questionnaires, provide past medical history, and demographic information. Local/PBRN study coordinators perform the study procedures and record baseline information into the electronic data capture (EDC) system. The study coordinators calculate a CAPTURE score for each participant. For patients in a practice randomized to CAPTURE+COPD education, their practitioner is provided with CAPTURE results for their patient. Practitioners at sites randomized to the COPD education only intervention are blinded to CAPTURE scores. Practitioners in both intervention arms are blinded to research spirometry results.

Based on the data collected at baseline, participants will be classified into the following groups for analyses:

| Cohort | Definition |
|------------------------------|---|
| CAPTURE+ | Participants with 
 • CAPTURE score ≥ 5, or • CAPTURE score of 2, 3, or 4 with a low PEF, defined as <350 L/min for males and <250 L/min for females |
| CAPTURE- | Participants with 
 • CAPTURE score < 2 or scores 2-4 with normal PEF (defined as ≥ 350 L/min for males and ≥ 250 L/min for females) |
| Spirometrically Defined COPD | Participants with abnormal spirometry, defined as post-bronchodilator $FEV_1/FVC <0.7$. If a participant is unable to complete a post-bronchodilator spirometry |

| | |
|--|---|
| | (refusal, technical error on the part of coordinator, etc.), and the pre-bronchodilator FEV_1/FVC is less than 0.65, the participant will be considered to have COPD for the purpose of follow-up in this study. |
| Clinically Significant COPD | Participants with abnormal spirometry, defined as spirometrically defined COPD plus at least one of the following: 
 • $FEV_1 < 60\%$ predicted or • ≥ 1 exacerbation like event within the past 12 months. |
| Mild COPD | Participants with spirometrically defined COPD plus both of the following: 
 • $FEV_1 \geq 60\%$ and • No prior history of ECOPD |

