13.1 SARS-COV-2 Impact on Study Enrollment, Follow-up and Power

We have performed additional analyses for the CAPTURE DSMB regarding the impact of SARS-COV-2 on study power for the cluster randomized clinical trial described in Aim 3 of the CAPTURE protocol, summarized in a Memo dated March 30, 2020. Sections of the memo relevant to the SAP are repeated below.

At the time of placing enrollment on hold, the CAPTURE study was ahead of enrollment projections with a goal of completion of all patient enrollment by January 31, 2021. Table 1 displays enrollment data for each of the CAPTURE study's six enrolling PBRNs as of March 19, 2020, the date the last of

the six PBRNs temporarily stopped enrollment.

Table 6.

| PBRN site | Date enrollment put on hold | Number of practices enrolled as of 19MAR2020 (goal) | Number of patients enrolled as of 19MAR2020 (goal) | Estimated date of resumption of enrollment |
|-----------|-----------------------------|---|--|--|
| A | 13MAR2020 | 15 (20) | 663 (1000) | Indeterminate |
| B | 16MAR2020 | 15 (20) | 750 (1000) | Indeterminate |
| C | 16MAR2020 | 9 (20) | 431 (1000) | Indeterminate |
| D | 19MAR2020 | 6 (8) | 280 (400) | Indeterminate |
| E | 13MAR2020 | 11 (20) | 468 (1000) | Indeterminate |
| F | 16MAR2020 | 12 (13) | 446 (650) | Indeterminate |

As of April 1, 2020, none of the sites has an estimate of when enrollment will be able to resume. This information will be added as soon as such information becomes available.

Projected Enrollment Impact

To facilitate planning, projections on patient and practice enrollment impacts for Aim 3 have been developed. These projections are based on several assumptions.

1. Monthly enrollment rates of 100 or 125 patients as continuation and 5 new practices enrolled per month, consistent with prior data.
2. Two, four and six-month delays in enrollment.

Table 7.

| Enrollment suspension length assumption | Enrollment re-start date | Enrollment rate/month | Total number of participants (practices) enrolled by 31JAN2021 | Total number of participants enrolled by 31MAR2021 |
|---|--------------------------|-----------------------|--|--|
| 2 months | 1-Jun-20 | 100 | 3850 (100) | 4050 |
| 4 months | 1-Aug-20 | 100 | 3650 (100) | 3850 |
| 6 months | 1-Oct-20 | 100 | 3450 (90) | 3650 |
| 2 months | 1-Jun-20 | 125 | 4050 (100) | 4300 |
| 4 months | 1-Aug-20 | 125 | 3800 (100) | 4050 |
| 6 months | 1-Oct-20 | 125 | 3550 (90) | 3750 |

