|----------|------|------|------|-------|-------|
| ICC=0.10 | 0.65 | 0.84 | 0.98 | >0.99 | >0.99 |
| ICC=0.15 | 0.55 | 0.76 | 0.95 | >0.99 | >0.99 |

However, we have important secondary analyses that include determining whether care is improved for patients who have spirometrically defined COPD. Based on data accumulated to date, we have a prevalence of roughly 2 spirometrically defined COPD patients per practice. These subsequent calculations demonstrate that based on 2 COPD patients/practice but with otherwise similar assumptions to Table 6, we would not be well powered for small effect sizes. Hence, while we would have important usable data should the study be unable to continue, the returns on investment made to date are far from fully realized. We strongly believe that all attempts should be made to complete the study as planned if we want to have the impact originally intended for this study, namely understanding whether screening benefits undiagnosed patients with COPD.

Table 11. Overall power to detect a difference in rate of meeting primary endpoint in CAPTURE group vs usual care, assuming 5% performance rate in usual care; 67 total practices; 2 COPD/practice

| Improvement over usual care | +7.5% | +10% | +15% | +25% | +50% |
|-----------------------------|-------|-------|------|------|-------|
| ICC=0.05 | <0.50 | <0.50 | 0.69 | 0.95 | >0.99 |
| ICC=0.10 | <0.50 | <0.50 | 0.67 | 0.95 | >0.99 |
| ICC=0.15 | <0.50 | <0.50 | 0.65 | 0.94 | >0.99 |

14 Reporting Conventions

P-values ≥ 0.001 will be reported to 3 decimal places; p-values less than 0.001 will be reported as " <0.001 ". The mean, standard deviation, and any other statistics other than quantiles, will be reported to one decimal place greater than the original data. Quantiles, such as median, or minimum and maximum will use the same number of decimal places as the original data. Estimated parameters, not on the same scale as raw observations (e.g., regression coefficients) will be reported to 3 significant figures.

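### The 300-800 clinically significant COPD cases expected in Protocol 9.1.1.1 and Table 9-3 are not supported by the interim COPD yield reported in SAP 13.1, so the stated precision for sensitivity is probably optimistic

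*Protocol*

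**What the plan says.** Protocol 9.1.1.1 plans to enrol about 5,000 patients "with the expectation that 300-800 of these will have previously undiagnosed clinically significant COPD". These cases are the denominator for sensitivity. Table 9-1 gives 95% half-widths by sample size, and the worked example uses 500 cases (90% ± 2.6%).

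Table 9-3 repeats 300-800 in its total column and splits it by subgroup, for example 54-144 Hispanic and 45-120 Black cases. Its caption describes the table as "assuming prevalence of obstructed individuals is between 6-16" percent. The caption also assumes that COPD which is not clinically significant is about equally common. Section 9.1.2.1 illustrates Hispanic sensitivity with about 100 cases (90% ± 5.9%) and expresses the belief that the subgroups will be large enough.

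SAP 13.1 reproduces a memo of March 2020. Its Table 6 lists enrolment by network under "Number of patients enrolled as of 19MAR2020 (goal") for the "six enrolling PBRNs as of March 19, 2020". On data to that date the memo says "we have a prevalence of roughly 2 spirometrically defined COPD patients per practice".

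SAP 6.1 defines clinically significant COPD as "Participants with abnormal spirometry, defined as spirometrically defined COPD plus at least one of the following": FEV1 below 60% predicted, or at least one exacerbation-like event. The protocol's definition likewise requires post-bronchodilator FEV1/FVC below 0.7. Under either document, clinically significant cases are a subset of spirometric cases.

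**The concern.** The protocol's minimum for the subset (300) is higher than the number the SAP's own yield projects for the whole set. Sensitivity is half of the Aim 1 primary endpoint, and its precision depends on the case count rather than on total enrolment. Protocol version 8.0 (July 2023) still carries 300-800, more than three years after the memo. A reader would therefore expect narrower intervals than the interim data suggest, most of all in the smaller ethnic subgroups, where sensitivity is a listed secondary endpoint.

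**Working it through.** **1. Reproduce the protocol's figures.**
- Cases: 0.06 × 5,000 = 300 and 0.16 × 5,000 = 800, as stated.
- No-COPD row of Table 9-3: 5,000 − 2 × 300 = 4,400 and 5,000 − 2 × 800 = 3,400, as stated.
- Table 9-1: the half-width 1.96 × √(p(1−p)/n) reproduces all 21 cells.

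The arithmetic is sound. The question is whether the assumed prevalence is.

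**2. Interim yield (SAP Table 6 and the memo text).**
- Patients: 663 + 750 + 431 + 280 + 468 + 446 = 3,038.
- Practices: 15 + 15 + 9 + 6 + 11 + 12 = 68, or 44.7 patients per practice. The memo's power calculations use 67, the practices it counts as having CAPTURE+ patients.
- Spirometric COPD: 2 × 67 = 134 or 2 × 68 = 136, which is 4.4% to 4.5% of 3,038.

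Two per practice is a working input in the memo. SAP Table 11 reproduces within 0.02 using it.

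**3. Projection to full enrolment**, as (cases per practice × practices) / 3,038 × N:

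| Cases per practice | N = 5,000 (67 or 68 practices) |
|---|---|
| 1.5 | 165-168 |
| 2 | 221-224 |
| 2.5 | 276-280 |

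The 1.5-2.5 range is an assumption about rounding. At the 4,800 participants given in Protocol 5.4 ("Approximately 4800 participants will be recruited from 100 primary care clinics affiliated with six PBRNs"), 2 per practice gives 212-215. Patients, not practices, are the scaling unit because practices were only partly filled; 2 × 100 practices would give 200.

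**4. What would be needed to reach 300.** There were 5,000 − 3,038 = 1,962 patients left to enrol.
- At 2 per practice so far: (300 − 136) / 1,962 = 8.4%, against 4.5% to date.
- At 2.5 per practice so far: (300 − 170) / 1,962 = 6.6%, against 5.6% to date.

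Both also require every spirometric case to be clinically significant.

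**5. Precision at 90% sensitivity**, 1.96 × √(0.09/n):

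| Cases | Half-width |
|---|---|
| 800 | ±2.1% |
| 500 (worked example) | ±2.6% |
| 300 | ±3.4% |
| 280 | ±3.5% |
| 220 | ±4.0% |
| 165 | ±4.6% |
| 110 | ±5.6% |

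The 110 row is half of 220, following Table 9-3's equal split between clinically significant and other COPD.

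**6. Subgroups, if cases follow Table 9-3's enrolment shares and all 220 are clinically significant.**
- Hispanic: 0.18 × 220 ≈ 40, half-width ±9.3%, against about 100 and ±5.9% in the example.
- Black: 0.15 × 220 = 33, half-width ±10.2%.

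**7. Table 9-3 caption against rows.** The rows use 6-16% for clinically significant COPD alone. With the equal-prevalence assumption, obstructed participants total 600-1,600, which is 12-32% of 5,000. The caption gives 6-16% as the prevalence of obstruction.

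**The case against.** Several points on the other side stand.

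- **It is not a calculation slip.** A reader might infer an arithmetic error, but 300-800 is exactly 6-16% of 5,000. It is a design expectation overtaken by later data.
- **220 is not a hard ceiling.** A reader might take it as an upper bound on clinically significant cases. Only the actual spirometric count bounds them. The 220 is a projection from one rounded phrase, divided by a patient total from another table. The memo does not say which patients its data covered. Spirometry is centrally graded, so the count may not cover all 3,038. The networks also differ: SAP 4.1 describes "100 primary care practices affiliated with seven practice-based research networks (PBRNs"), while the memo covers six.
- **The subgroup counts are not maxima.** They assume equal prevalence across groups and an unchanged enrolment mix.
- **The consequence is limited.** Aim 1 is estimation, with no test or success threshold, and Table 9-1 already prints half-widths at 250, 100 and 50. Against the bottom of the stated range, the best-case change is from ±3.4% to about ±4.0%.
- **The SAP partly discloses it.** The memo says that analyses in COPD patients would be poorly powered for small effects. That remark concerns Aim 3 secondary analyses, not Aim 1 precision.

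These points limit how far the finding goes, but they do not remove the conflict: no yield within the assumed 1.5-2.5 range, carried forward, reaches 300.

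**Conclusion.** The concern holds as an unsupported planning figure, with minor to moderate severity. On the trial's own March 2020 yield, about 220 spirometric cases of any severity would be expected in 5,000 (165-280 under the rounding assumption). The minimum of 300 for the clinically significant subset is therefore not supported. The half-width for sensitivity would be about ±4.0% at best and wider if only some of those cases are clinically significant; that share is not in the documents. The Hispanic example of about 100 cases would be nearer 40 on the Table 9-3 shares.

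This rests on three assumptions: the later yield matches the yield to March 2020, the per-practice figure applies to the 67 or 68 practices then enrolled, and, for subgroups, cases follow enrolment shares. It does not show that the final count fell below 300, since later practices could differ. It does not affect specificity precision or the power of the Aim 3 primary analysis, which rests on CAPTURE+ counts.

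The caption mismatch in Table 9-3 is separate. It is visible on the page and needs no projection.

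**What to change.** Change protocol wording only; SAP 4.1 places Aim 1 outside the SAP's scope.

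1. In 9.1.1.1, keep 300-800 but label it the original design assumption. State that the March 2020 yield is lower and give the resulting half-widths for sensitivity, using the data coordinating center's baseline case counts, pooled across arms, where available.
2. Correct the Table 9-3 caption so that 6-16% refers to clinically significant COPD. The no-COPD row can stay: it is consistent with the stated equal-prevalence assumption.
3. In 9.1.2.1, qualify the sentence on subgroup size. Say that at the lower yield, sensitivity in the smaller subgroups (Hispanic, Black) will be less precise than the example with about 100 cases.

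The cost is a few sentences and one tabulation of baseline counts. Enrolment, data collection and analysis stay as they are. The stated precision becomes less favourable.

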9.1.1.2 ADOPTION AND IMPLEMENTATION OF THE CAPTURE TOOL IN PRIMARY CARE PRACTICE

Primary Hypothesis 2: *A COPD case finding methodology using a validated one-page, five-item questionnaire with selective PEF measurement (CAPTURE) can be incorporated into the clinical practice patterns, clinical workflow, communication and practice-based quality improvement paradigms of a variety of primary care clinical settings.*

Aim 2 is a qualitative study to determine the efficacy of workflow integration of the CAPTURE tool. Statistical analysis of the clinician questionnaire will involve simple sums of each item and reviewing answers across practices and region. Standard frequencies for questions will be developed to examine patterns in responses.

The clinician focus groups will be conducted on-site at each practice at a time convenient for the participating clinicians. The number of prescribing and non-prescribing clinicians will equal 15 per practice and is based on interest with a maximum of 8 prescribing clinicians/practice. The sample size will follow a basic qualitative sampling standard of interviewing to redundancy or saturation. The number of clinicians to be interviewed (up to n=15 in each practice) is estimated based on achieving concept saturation. Reflecting regional primary care practice norms and to bolster concept saturation, PBRN Aim 2 coordinator focus group discussion participation is encouraged for very small practices where the participating prescribing and non-prescribing clinician total is less than or equal to 4. For all practice focus groups questions will explore the described Aim 2 CAPTURE RE-AIM concepts, barriers to implementation of the CAPTURE tool at other practice sites, standard processes for COPD and respiratory care diagnosis and management for each clinical role within the practice, and perception of quality improvement methods at each practice. Clinician focus groups are conducted on-site at each of the 10 practices.

Transcripts of clinician focus groups will all be digital and entered into a qualitative data analysis program, NVivo for Mac. This program allows for an investigation of the salience, patterning, and contexts of key discourse items. Grounded theory methods will be used to identify and label recurrent themes and concepts within textual materials. Texts will be examined line-by-line, key phrases assigned tentative category labels, and coded passages grouped under the themes of feasibility, barrier and utility. The analyses will look for “traces” in dialogue, including repetitions, key words, evaluation statements, and metaphors. Change in salience, patterning, or content of key themes will provide further empirical evidence regarding the efficacy of our program’s efforts to impact community norms and behaviors. An audit trail will be maintained to document the position of text material from which codes and themes are developed. We will use word/code counts of repetitive themes and concepts to indicate patterns. By allowing for open-ended responses, the narratives and notes will allow us to

capture significant changes in participants' attitudes or behaviors. Codes and themes will be discussed iteratively with the research team members to hone definitions and assure consistency of interpretation. We will establish a coding dictionary and all interviews will be coded using the complete set of themes. Two independent coders will code each document to assure inter-coder reliability. Preliminary results will be shared with our Aim 2 research team and will inform the development of the case studies for the latter part of the project.

9.1.1.3 PRACTICE BEHAVIOR IN SITES WITH VERSUS WITHOUT CAPTURE EDUCATION AND PATIENT LEVEL CAPTURE DATA PROVIDED

Primary Hypothesis 3: *Sites where basic COPD and CAPTURE education are provided to clinicians, along with patient level CAPTURE data, will have a higher probability than control sites (i.e., those receiving only basic COPD education) of meeting the composite endpoint in their CAPTURE+ patients within 12 months of baseline.* From medical record review and follow-up patient survey responses, the composite endpoint is met if one of the following is recorded: (1) referral for or completion of clinical spirometry testing, 2) new clinical diagnosis of COPD, 3) newly prescribed respiratory medication (long acting bronchodilator or anti-inflammatory for respiratory condition), 4) referral to a specialist for respiratory evaluation/ treatment, or 5) referral for or completion of pulmonary rehabilitation.

The study will enroll 50 CAPTURE practices and 50 control practices; each practice will enroll 50 patients (for a total of approximately 5,000 patients). We project that within each practice, there will be at least 5 patients previously undiagnosed with COPD who have a CAPTURE+ screening result. The primary analysis will be to compare the average proportion of CAPTURE+ patients per practice that meet the composite endpoint in the two intervention arms. For power and sample sizes computations, this is a cluster randomized trial of n=50 clusters (practices) per intervention arm with 5 CAPTURE+ patients per cluster (practice). The primary power calculation is based on comparing the average cluster sample proportion (average proportion of CAPTURE+ patients per practice meeting composite endpoint) between intervention arms. Table 9-2 displays power for a two-sample test comparing average cluster sample proportions, accounting for possible intra-cluster correlation coefficient (ICC) values of 0.05, 0.10 and 0.15 that are typically seen in cluster randomized trials of behavioral interventions (<https://www.abdn.ac.uk/hsru/research/research-tools/study-design/>). These calculations assume a type I error of 5% and that the control arm meets the composite endpoint in 5% of CAPTURE+ patients and the CAPTURE arm meets the composite endpoint in higher percentages (columns of Table 9-2). There will be variability in the actual number of CAPTURE+ patients per practice. It is standard practice to inflate the number of needed clusters by 12% to account for this extra source of variability. Therefore, our power calculations are based on 44 clusters per intervention arm.

Table 9-2. Overall power to detect a difference in rate of meeting primary endpoint in CAPTURE group (50 practices/clusters) vs usual care (50 practices/clusters), assuming 5% performance rate in usual care; 50 patients total / practice; assuming 10% prevalence gives 5 CAPTURE+/practice

| Improvement over usual care | +7.5% | +10% | +15% | +25% | +50% |
|-----------------------------|-------|------|------|-------|-------|
| ICC=0.05 | 0.72 | 0.89 | 0.99 | >0.99 | >0.99 |
| ICC=0.10 | 0.65 | 0.84 | 0.98 | >0.99 | >0.99 |
| ICC=0.15 | 0.59 | 0.79 | 0.97 | >0.99 | >0.99 |

